6.2.1.5 Criteria for Pausing or Stopping

If 1 of the criteria described below is reached, further enrollment of subjects will be suspended pending assessment by the Sponsor:

- any treatment-related death, or

- any Grade 4 CRS per ASTCT consensus criteria, that does not resolve to Grade 1 within 72 hours despite therapy, or
- any Grade 4 neurotoxicity per ASTCT ICANS consensus grading criteria for adults, that does not resolve to Grade 1 within 72 hours despite therapy, or
- evidence of any T cell proliferative disorder, or.
- any grade 3 or higher GVHD or Grade 2 GVHD that does not resolve to Grade 1 in response to systemic steroid therapy within 7 days.

If at the time enrollment is paused, and a subject has received lymphodepleting chemotherapy but has not yet received NTLA-5001, treatment with a lower dose of NTLA-5001 given to a prior cohort may be considered with agreement of the Sponsor and investigator.

An assessment of all available information will be completed by Sponsor in conjunction with the DMC. Resumption of enrollment and dosing will be decided by the Sponsor with recommendation from DMC.

6.2.2 Selection of Dose for Expansion

At the completion of dose escalation in each Arm, all subject clinical data will be reviewed by the DMC to recommend a dose or range of doses that are suitable for the safety expansion cohort. Selection of dose for expansion will be decided by the sponsor.

6.2.3 Dosage Adjustments, Delays, Rules for Withholding or Restarting, and Permanent Discontinuation

Study drug will be administered as a single dose so there will be no dose adjustments.

The infusion of study drug will be slowed or stopped in the event of an infusion-related reaction (IRR). Following resolution of a mild or moderate IRR that required interruption or slowing of study drug infusion, resumption of the infusion may occur at the investigator's discretion at a slower infusion rate. However, the time from opening of thawed study drug vials through completion of the infusion may not exceed [REDACTED]

Study drug administration will not be resumed for any subject following a severe IRR until the case is discussed with the Medical Monitor.

Subjects who receive a partial infusion will continue to attend all study visits and have all tests performed per the SoA (Section 1.3).

6.3 Preparation/Handling/Storage/Accountability

NTLA-5001 is a colorless to slightly yellow, clear to slightly cloudy cell suspension supplied in [REDACTED] bags at a targeted concentration of [REDACTED]. Fill volumes will vary from subject to subject based on cohort dose level and subject yield. The infusion bags are to be stored at $\leq -150^{\circ}\text{C}$ in a liquid nitrogen vapor phase container. For administration, NTLA-5001 will be thawed and delivered by IV infusion.

The study drug dose will be prepared by a clinical site pharmacist or member of the site cell laboratory for infusion. NTLA-5001 will be administered by IV infusion at 10-20 ml/min. Total

study drug preparation and administration time from puncture of study drug infusion bag through completion of infusion may not exceed [REDACTED]

Details regarding the vein-to-vein shipping, manufacturing process, tracking and storage, study drug preparation and administration will be provided in the Cell Therapy Manual.

The investigator is to ensure per International Council for/Conference on Harmonisation (ICH) Good Clinical Practice (GCP) Guidelines that study drug deliveries from the Sponsor are received by the investigator/or designee and that:

- Such deliveries are recorded,
- Study drug is handled and stored according to labeled storage conditions,
- Study drug with appropriate expiry/retest and is only dispensed to study subjects in accordance with the protocol, and
- Any unused study drug or expired drug should be destroyed in accordance with institutional guidelines.

Drug inventory and accountability records for the study drugs will be kept by the investigator/or designee. Study drug accountability throughout the study must be documented and reconciled. The following guidelines are therefore pertinent:

- The investigator agrees not to supply study drugs to any persons except the eligible subjects enrolled in this study in accordance with the protocol.
- The investigator or designee will keep the study drugs in a pharmacy or other locked and secure storage facility under controlled storage conditions, accessible only to those authorized by the investigator to dispense these test drugs.
- A study drug inventory will be maintained by the investigator or designee. The inventory will include details of material received and a clear record of what study drug was used.
- At the conclusion or termination of this study, the investigator or designee agrees to conduct a final drug supply inventory and to record the results of this inventory on the Drug Accountability Record. It must be possible to reconcile delivery records with those of used and/or returned medication. Any discrepancies must be accounted for and documented. Appropriate forms of deliveries and returns must be signed by the site staff delegated this responsibility.

6.4 Measures to Minimize Bias: Randomization and Blinding

6.4.1 Randomization

Randomization is not used in this study.

6.4.2 Masking

This is an open-label study. Masking is not applicable.

6.5 Study Treatment Compliance

Study drug administration (a single IV infusion) will be done at the clinic under medical supervision. The date and time of the dose administered in the clinic will be recorded in the source documents and recorded in the electronic Case Report Form (eCRF). See the Cell Therapy Manual for details on preparation and administration of the study medication.

6.6 Concomitant Therapy

At the time of NTLA-5001 administration, tocilizumab (8 mg/kg IV) must be available on site.

After the Day 28 visit and assessments, AML therapy may be initiated for subjects not receiving benefit at the discretion of the investigator.

Any medication or vaccine (including over the counter or prescription medicines, vitamins, and/or herbal supplements) that the subject is receiving at the time of enrollment or receives during the study must be recorded along with:

- reason for use
- dates of administration including start and end dates
- dosage information including dose and frequency

The Medical Monitor should be contacted if there are any questions regarding concomitant or prior therapy.

6.6.1 Prohibited Medications/Procedures

Prohibited medications include:

- granulocyte-macrophage colony-stimulating factor (GM-CSF)
- granulocyte colony-stimulating factor (GCSF) is prohibited from 72 hours of prior to lymphodepleting chemotherapy through the Week 2 visit
- long-acting GCSF is prohibited from 2 weeks prior to lymphodepleting chemotherapy through the Week 2 visit
- steroids are prohibited within 72 hours of lymphodepleting chemotherapy, except for physiologic steroid replacement with ≤ 0.2 mg/kg/day methylprednisolone or equivalent
- live vaccine administration from the time of lymphodepleting chemotherapy through infusion of NTLA-5001, for at least three months after NTLA-5001 and until immune recovery following treatment

Additionally, subjects must agree not to participate in another interventional study for a minimum of 28 days post dosing of NTLA-5001. Additional investigational interventions could confound the primary objective of the study to assess safety of NTLA-5001.

6.7 Toxicity Management

Recommendations for management of potential toxicities of NTLA-5001 are provided, including specific agents to be used, doses and intervals, and lines of therapy. These recommendations may be modified by the investigator to accommodate existing institutional guidelines for management of cell therapy toxicities and variations in global standard-of-care practices.

6.7.1 Acute Infusion Reaction

Acetaminophen/paracetamol and diphenhydramine /H1 antihistamine may be repeated every 6 hours as needed. If the subject continues to have fever, a course of nonsteroidal anti-inflammatory medication may be prescribed. It is recommended that subjects not receive corticosteroids except in the case of life-threatening emergency, because this may adversely affect NTLA-5001 cells. For additional notes regarding interruption of study drug during an acute infusion reaction, see Section 6.2.3.

6.7.2 Cytokine Release Syndrome

Cytokine release syndrome (CRS), when present, typically manifests in the first days after cellular therapy. CRS may include a prodromal syndrome characterized by flu-like syndrome with, fatigue, headache, arthralgia, myalgia, and malaise, which is then followed at CRS onset by fever, hypoxia, and/or mild hypotension. In severe cases, CRS may be characterized by hemodynamic instability and organ dysfunction. Routine monitoring during hospitalization, should include vital sign assessment every 4 hours and evaluation for CRS symptoms at least twice a day. Subjects with CRS should have laboratory assessments including daily complete chemistry panel, albumin, lactose dehydrogenase (LDH), liver enzymes, bilirubin, and coagulation panel with prothrombin time, partial thromboplastin time, fibrinogen, and D-dimer, C-reactive protein and ferritin. Adverse events of CRS are graded according to the ASTCT consensus grading scale (Section 13.5). Sites with local Standard Operating Procedures for the treatment of CRS should follow those protocols. For other sites, suggested treatment is below:

- **Prodromal symptoms** should be treated with symptomatic support and observation. Infection should be considered in the differential diagnosis and surveillance cultures or prophylactic antibiotics prescribed as warranted.
- **Initial mild signs of fever, hypoxia, and/or mild hypotension** should be treated with oxygen, antipyretics, fluids, low-dose vasopressor support (vasopressin monotherapy, dopamine monotherapy < 10 ug/kg/min), and tocilizumab (8 mg/kg IV).
- **For initial symptoms that persist beyond 12-18 hours**, subjects should be treated with additional tocilizumab a minimum of 8 hours after the first dose which may be continued for 4 doses. For subjects with symptoms that do not respond to tocilizumab, additional interleukin-6 (IL-6) directed therapy (siltuximab 11 mg/kg) should be considered.
- **More severe symptoms than fever, hypoxia, and/or mild hypotension** typically include respiratory distress despite supplemental oxygen or hemodynamic instability. Subjects should be carefully evaluated for infection and empiric therapy should be considered. Such symptoms should be treated with continued IL-6 directed therapy, and corticosteroids (methylprednisolone 2 mg/kg x 1 followed by 0.5 mg/kg q6h; or dexamethasone

0.4 mg/kg x 1 followed by 0.1 mg/kg q6h; or equivalent). Steroids should be tapered to off within 1 week. Coagulopathy should be treated with fresh frozen plasma or cryoprecipitate. Hypoxia may require high-flow oxygen by face mask or positive airway pressure ventilation. High dose vasopressors for hemodynamic support with norepinephrine, dopamine > 10 µg/kg/min, or phenylephrine may be needed.

- **For subjects with severe symptoms that are persistent 24 hours after steroid administration**, etanercept (50 mg subcutaneous [SC]) or anakinra (100 mg SC) should be considered. Subjects with persistent life-threatening symptoms may require anti-T cell therapy such as such as alemtuzumab (12 mg IV over 4 hours once daily [QD] x 5d), high dose cyclophosphamide, or antithymocyte globulin (ATG) (2 mg/kg/day IV).

The need for positive pressure ventilation or the need for multiple vasopressors in the presence of fever $\geq 38^{\circ}\text{C}$ constitutes Grade 4 CRS. Grade 4 CRS should be reported immediately to the medical monitor. If the event does not resolve to Grade 1 CRS within 72 hours, a criterion for pausing study enrollment is reached.

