6.2.1.2 Definition of a Dose-limiting Toxicity

DLTs are defined as events with onset within 28 days of infusion as follows:

- Any Grade 4 CRS per American Society for Transplantation and Cellular Therapy (ASTCT) consensus criteria, and Grade 3 CRS that does not resolve to Grade 2 within 72 hours
- Any Grade 3/4 neurotoxicity per ASTCT immune effector cell-associated neurotoxicity syndrome (ICANS) consensus grading criteria for adults
- Any Grade 4 acute GVHD of any duration; Grade 2 or 3 acute GVHD requiring systemic steroid treatment that does not resolve to \leq Grade 1 within 7 days.
- Acute infusion reaction: Reactions related to NTLA-5001 occurring within 2 hours of infusion that are not reversible to \leq Grade 2 within 24 hours.
- Grade 4 neutropenia or thrombocytopenia lasting more than 28 days that is not attributable to underlying disease or lymphodepletion chemotherapy
- Other severe organ toxicity that is not attributable to underlying disease or lymphodepletion chemotherapy as follows: Grade 4 toxicity that is a cardiac disorder, hepatobiliary disorder, renal disorder, respiratory disorder, or vascular disorder (per CTCAE); Grade 3 cardiac, respiratory, or vascular disorder that does not resolve to Grade 2 or lower within 72 hours; or Grade 3 hepatobiliary or renal disorder that does not resolve to Grade 2 or lower within 7 days.
- Grade 5 events without clinical or radiological evidence of disease progression which are related to NTLA 5001.

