13.5 Appendix 5 CRS and ICANS Grading

CRS Consensus Grading

CRS Parameter	Grade 1	Grade 2	Grade 3	Grade 4
Fever [*]	Temperature $\geq 38^{\circ}\text{C}$	Temperature $\geq 38^{\circ}\text{C}$	Temperature $\geq 38^{\circ}\text{C}$	Temperature $\geq 38^{\circ}\text{C}$
With Hypotension	None	Not requiring vasopressors	Requiring a vasopressor with or without vasopressin	Requiring multiple vasopressors (excluding vasopressin)
And/or [†] Hypoxia	None	Requiring low-flow nasal cannula [‡] or blow-by	Requiring high-flow nasal cannula [‡] , facemask, nonrebreather mask, or Venturi mask	Requiring positive pressure (eg, CPAP, BiPAP, intubation and mechanical ventilation)

Organ toxicities associated with CRS may be graded according to CTCAE v5.0 but they do not influence CRS grading.

^{*} Fever is defined as temperature $\geq 38^{\circ}\text{C}$ not attributable to any other cause. In patients who have CRS then receive antipyretics or anticytokine therapy such as tocilizumab or steroids, fever is no longer required to grade subsequent CRS severity. In this case, CRS grading is driven by hypotension and/or hypoxia.

[†] CRS grade is determined by the more severe event: hypotension or hypoxia not attributable to any other cause. For example, a patient with temperature of 39.5°C , hypotension requiring 1 vasopressor, and hypoxia requiring low-flow nasal cannula is classified as grade 3 CRS.

[‡] Low-flow nasal cannula is defined as oxygen delivered at ≤ 6 L/minute. Low flow also includes blow-by oxygen delivery, sometimes used in pediatrics. High-flow nasal cannula is defined as oxygen delivered at >6 L/minute.

ICANS Consensus Grading for Adults

Neurotoxicity Domain	Grade 1	Grade 2	Grade 3	Grade 4
ICE score [*]	7-9	3-6	0-2	0 (patient is unarousable and unable to perform ICE)
Depressed level of consciousness [†]	Awakens spontaneously	Awakens to voice	Awakens only to tactile stimulus	Patient is unarousable or requires vigorous or repetitive tactile stimuli to arouse. Stupor or coma
Seizure	N/A	N/A	Any clinical seizure focal or generalized that resolves rapidly or nonconvulsive seizures on EEG that resolve with intervention	Life-threatening prolonged seizure (>5 min); or Repetitive clinical or electrical seizures without return to baseline in between
Motor findings [‡]	N/A	N/A	N/A	Deep focal motor weakness such as hemiparesis or paraparesis

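### Section 6.7.2 restates Grade 4 CRS in words that conflict with the Appendix 5 grading table on which the DLT and pausing rules rely

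*Protocol*

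**What the plan says.** Protocol Section 6.7.2 closes with its own statement of Grade 4 CRS: "The need for positive pressure ventilation or the need for multiple vasopressors in the presence of fever" of at least 38 °C. The same paragraph asks for immediate notice to the medical monitor and then adds: "If the event does not resolve to Grade 1 CRS within 72 hours, a criterion for pausing study enrollment is reached".

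The grading table in Protocol Section 13.5 (Appendix 5) is worded differently in two respects.

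- **Vasopressors.** The Grade 4 hypotension entry is "Requiring multiple vasopressors (excluding vasopressin", closing the bracket there. The Grade 3 entry is "Requiring a vasopressor with or without vasopressin".
- **Fever.** Once a subject with CRS has had antipyretics, or anticytokine therapy such as tocilizumab or steroids, "fever is no longer required to grade subsequent CRS severity".

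Two decision rules depend on the grade. Section 6.2.1.2 makes a DLT of "Any Grade 4 CRS per American Society for Transplantation and Cellular Therapy (ASTCT) consensus criteria", and of Grade 3 CRS only when it has not come down to Grade 2 by 72 hours. Section 6.2.1.5 pauses enrollment for "any Grade 4 CRS per ASTCT consensus criteria, that does not resolve to Grade 1 within 72 hours despite therapy".

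Protocol Section 8.5.2, SAP Section 6.5.1 and an earlier paragraph of Section 6.7.2 itself all send CRS grading to the ASTCT scale. The two protocol sections cite Section 13.5 for it.

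**The concern.** In this trial the step from Grade 3 to Grade 4 CRS decides whether a short-lived event is a DLT, and whether a persisting one can pause enrollment. Section 6.7.2 is the section a treating physician is likely to have open during a CRS event. It is also where the instruction to call the medical monitor sits. If its Grade 4 sentence does not match the table, an investigator who grades from it can over-call or under-call the event.

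Dose decisions rest on groups of three, so one event matters. Under Section 6.2.1.3, 0/3 permits escalation, 1/3 adds three subjects, and 2/3 stops escalation. In an expanded group the same single event separates 1/6 from 2/6. Under Section 6.2.1.4, a single Arm 1 DLT at the current dose also rules out simultaneous escalation of the arms.

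**Working it through.** The plan states no figure to reproduce, so the check sets the two texts side by side.

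**1. Vasopressin (the firm conflict).** Take a febrile subject on norepinephrine plus vasopressin, without positive pressure ventilation. Section 6.7.2 itself lists vasopressin monotherapy as low-dose vasopressor support at the first mild signs and names norepinephrine for more severe symptoms, so the combination can arise by following that section. Two vasopressors with fever are Grade 4 by the 6.7.2 sentence. By Section 13.5 this is one vasopressor with vasopressin, hence Grade 3. Applying Sections 6.2.1.2 and 6.2.1.5, and assuming no other DLT or pausing criterion is met:

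| Course over 72 hours | Graded by the 6.7.2 sentence | Graded by Section 13.5 |
|---|---|---|
| Down to Grade 1 | DLT, no pause | no CRS DLT, no pause |
| Down to Grade 2, not Grade 1 | DLT, pause | no CRS DLT, no pause |
| Not down to Grade 2 | DLT, pause | DLT (unresolved Grade 3), no pause |

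DLT status differs in the first two rows and pausing status in the last two.

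**2. Fever (the softer conflict).** Take a subject now afebrile after antipyretics, tocilizumab or steroids, on two vasopressors other than vasopressin. Section 13.5 gives Grade 4, hence a DLT. The 6.7.2 sentence requires fever and does not reach this subject. With positive pressure ventilation in place of two vasopressors, the answer depends on parsing. If fever qualifies both limbs of the sentence, the texts differ. If it qualifies only the vasopressor limb, they agree.

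**3. All combinations.** Cross fever now (2 levels), prior treatment (2), number of non-vasopressin vasopressors (0, 1, 2), vasopressin (2) and positive pressure (2): 2 × 2 × 3 × 2 × 2 = 48. Drop the 1 × 1 × 3 × 2 × 2 = 12 with neither fever nor prior treatment, leaving 36.

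- Fever qualifies both limbs: 2 vasopressin cases + 8 afebrile treated cases = 10 of 36 disagree.
- Fever qualifies the vasopressor limb only: 2 + 2 = 4 of 36 disagree.

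These count combinations and are not event probabilities. Disagreement runs in both directions under either parsing.

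**4. Scale of a shift in the counted DLT rate.** Under the Section 6.2.1.3 rule, P(escalate) = (1−p)³ + 3p(1−p)⁵. The documents give no DLT rate and no frequency of reclassification. The base rates and the added 5 and 10 points below are assumptions.

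| Base p | At base | +5 points | +10 points |
|---|---|---|---|
| 10% | 0.906 | 0.814 | 0.709 |
| 20% | 0.709 | 0.600 | 0.494 |
| 30% | 0.494 | 0.396 | 0.309 |

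**The case against.** The strongest reply is that Section 13.5 plainly governs. DLTs are defined only in Section 6.2.1.2, and pausing is set in Section 6.2.1.5 and repeated in the synopsis. All of these name the ASTCT criteria, and Section 6.7.2 never mentions DLTs. Section 6.7 offers recommendations that investigators may adapt. This stands. A reader might infer that the protocol holds two competing DLT definitions, but the documents do not support that. What remains is a sentence that states a grade threshold, triggers immediate reporting and points to the pausing criterion, and that disagrees with the governing table.

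Other points also narrow the concern:

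- **The verb.** *Constitutes* may state only a sufficient condition. That weakens the fever conflict. It does not help with vasopressin, because the sentence then declares sufficient for Grade 4 what the table places at Grade 3.
- **Other DLT routes.** Section 6.2.1.2 also counts certain Grade 4, and unresolved Grade 3, cardiac, respiratory and vascular disorders not attributable to disease or lymphodepletion. Some misgraded CRS would be caught there. The pausing list has no matching organ-toxicity item.
- **Data review.** Under Section 6.2.1.1, the sponsor's medical and safety leads and the treating investigators review all data before escalation. This could correct a misgrade, but it comes after the moment for immediate reporting.
- **Frequency.** Because Section 6.7.2 suggests antipyretics and tocilizumab at the first mild signs, a reader might infer that most subjects who worsen fall where the texts differ. No figure supports that. Prior treatment alone does not separate the texts: the subject must also be afebrile and meet a Grade 4 limb, or be on one vasopressor plus vasopressin. The suggested sequence is also only for sites without their own procedure.
- **Termination.** SAP Section 7 records 2 subjects treated when the study was stopped, too few to complete even one group of three.

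**Conclusion.** The conflict is real and confined to one sentence. On vasopressin it holds under every reading. It changes CRS DLT status when the event comes down to Grade 2 within 72 hours and no other DLT criterion is met, and it changes pausing status when the event does not come down to Grade 1 within 72 hours. On fever it holds for two non-vasopressin vasopressors if the sentence is taken as the full definition. The afebrile ventilated subject is a conflict under only one parsing and should not be cited as certain.

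The exposure is misapplication at a site when grading, reporting to the medical monitor or judging the pausing criterion. Its size is one event in a group of three, in either direction, with unknown frequency. The escalation probabilities above are illustrative only. With 2 subjects treated, the remaining effect is on the accuracy of any reported CRS grade and of the DLTs that SAP Sections 6.1 and 6.5.1 still flag and count, and on any reuse of the text. It is worth correcting but does not put the design in doubt. No view is taken here on which clinical definition is right.

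**What to change.** Reconcile the Grade 4 sentence in Section 6.7.2 with Section 13.5 so that a single Grade 4 CRS definition serves reporting to the medical monitor, DLT assessment and the pausing rule. Section 6.7.3 offers a drafting model: for ICANS it gives the same reporting and pausing instruction without restating what Grade 4 is.

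For the data in hand, check any reported CRS grade, and any DLT flag that follows from it, against that single definition before the SAP listings and adverse event summary are finalised.

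The cost is one sentence in an amendment, or in the template if the text is reused, and a check of the CRS records of 2 treated subjects.
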